5.2.8. Analysis Windows and Definitions

The following visit windows were defined per protocol for follow-up:

Week -1	Week 4	Week 8	Month 3	Month 6	Year 1 and 2
(- 7 days)	(28 days)	(56 days)	(90 days)	(180 days)	(365 and 730 days)
± 2 days	±7 days	±7 days	± 2 weeks (14 days)	± 4 weeks (28 days)	± 8 weeks (56 days)

For the day of the procedure (Day 0), flexibility in scheduling is permitted (up to 1 week), e.g., due to cath lab availability, based on physician discretion and with careful consideration of subject safety, thus data collected at the Week -1 visit will be acceptable if the day of procedure is extended by 1 week such that values up to 16 days (14+2 days) prior to procedure will be considered valid reading for analysis of baseline measures. If multiple baseline values are present prior to procedure, the valid reading that is closest to the day of procedure within window will be used.

For the purposes of statistical analysis, the 8-week window will be extended to -15 and +30 days (i.e., the window for valid data will range from 41 to 86 days) allowing blood pressure measures collected within a reasonable time frame but beyond the protocol defined window to be analyzed, provided that the subject remains off antihypertensive medication prior to the visit assessments at 8 weeks.

A table summarizing visit compliance will be included as part of the overall subject disposition.

5.3. Patient Disposition, Demographics and Other Baseline Characteristics

A tabulation of patient disposition will be presented including number treated, number completing each visit and number of withdrawals and lost to follow-up, including primary reason for withdrawal as documented on the case report form.

Baseline demographics and medical history will be summarized for the ITT, PP and Safety analysis sets.

5.3.1. Listing of Individual Data

A by-patient listing of key demographic data and medical history will be presented.

5.4. Primary Endpoints

The primary efficacy endpoint will be summarized in the ITT analysis set and the PP analysis set (if it differs from ITT). For the primary efficacy endpoint analysis, the primary population for analysis is ITT, while the PP population is considered supportive (for sensitivity analyses).

5.4.1. Primary Efficacy Endpoint

The mean change in 24-hour ambulatory SBP from baseline to 8 weeks post-treatment will be presented in each group. The difference between groups will be summarized and compared using ANCOVA with adjustment for the baseline 24-hour ambulatory SBP.

The protocol defined window for the 8-week (56 day) visit is ± 7 days. For the purposes of analysis, measurements obtained within -15 days or ± 30 days (i.e., between 41 and 86 days) will be considered valid and will be analyzed as part of the primary endpoint analysis, provided that the subject remained off antihypertensive medication prior to collection of ABPM.

For the primary analysis, all available data will be used. There will be no imputation of data at 8 weeks. This analysis will be repeated in the PP analysis set.

In addition to the primary analysis, the following secondary and sensitivity analyses will be conducted:

- 1. Subjects who meet the protocol defined criteria for antihypertensive drug treatment and receive treatment within the 8 weeks prior to assessment of the primary endpoint will have their 8-week value imputed with their baseline value of ABPM.
- 2. Subjects who meet the protocol defined criteria for antihypertensive drug treatment and receive treatment within 8 weeks will be removed from the analysis.
- 3. Subjects who receive antihypertensive treatment within 8 weeks for any reason or in whom antihypertensive medications are detected via compliance samples will be removed from the analysis.
- 4. Missing data at 8 weeks will be imputed via multiple imputation techniques. The following covariates will be considered for the imputation: treatment group, age, gender, history of diabetes, BMI, anatomy defined by length from ostium to bifurcation, number of medications at baseline, baseline office systolic pressure, 8-week office systolic pressure, baseline 24-hour ambulatory SBP. These factors were chosen based on clinical experience and recent literature (Fengler, 2016) (Id, 2016) (Kandzari, 2015).
- 5. Missing data at 8 weeks and data for those subjects who meet the protocol defined criteria for antihypertensive drug treatment and receive treatment within 8 weeks will be imputed via multiple imputation techniques.

An additional exploratory analysis will be conducted, which combines the treatment failures (subjects receiving rescue medication) with the continuous 24-hour ambulatory SBP measurement in a hierarchical fashion using the approach described in Finkelstein and Schoenfeld (1999) and later adapted to the Win Ratio by Pocock (2012). Using this approach, each subject is compared to every other subject first as to whether or not the subject received rescue medication. If both subjects did or did not receive rescue medication (i.e., there is a tie), then the subjects will have their change in 24-hour ambulatory SBP at 8 weeks compared. A score of -1 will be assigned to a loss and a score of +1 will be assigned to a win. For example:

- If Subject A receives rescue medication within 8 weeks and Subject B does not, Subject A loses (score -1), and Subject B wins (score +1)
- If neither receive rescue medication within 8 weeks, then if Subject A has a larger reduction in 24-hour ambulatory SBP at 8 weeks compared to Subject B, then Subject A wins (score +1) and Subject B loses (score -1).

After all between-subject comparisons have been performed, scores will be summed to obtain a cumulative score for each subject, and the scores between treatment groups will be compared using the Mann-Whitney U test. The resulting p-value will be presented. The win ratio will also be presented. It is calculated as number of "wins" divided by the number of losses out of all comparisons of intervention to sham subjects.

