5.2.3. Handling of Dropouts or Missing Data

For the primary efficacy endpoint analysis, all available data will be used. As additional analyses, patients who meet the protocol defined criteria for antihypertensive drug treatment within the 8 weeks prior to assessment of the primary endpoint will be assigned their baseline value of ABPM at 8 weeks. Additional sensitivity analyses will be conducted removing those

subjects who receive antihypertensive treatment within 8 weeks. Also, as a secondary sensitivity analysis, missing data will be imputed via multiple imputation techniques.

There will be no imputation of data for secondary efficacy endpoints or other endpoints; only available data will be used, with the exception of analyses at 8 weeks for subjects receiving protocol defined antihypertensive therapy within 8 weeks. Analyses will be conducted with all available data and only in subjects who did not receive antihypertensive treatment between baseline and 8 weeks.

This study allows for cross-over of control subjects once the participant has passed the 1-year study visit. Subjects who cross-over will be considered withdrawn from the main study as of the day of their cross-over procedure and will no longer be analyzed with the main study cohort (i.e., their data will be missing for any subsequent scheduled study visits).

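### SAP 5.4.1 attaches its off-drug condition to the whole 8-week window, against its own all-available-data rule, and one primary-endpoint subgroup is formed by drug need after the procedure

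*SAP*

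**What the plan says.** **Primary analysis.** SAP 5.4.1 restates the protocol window for the 8-week visit (56 days ± 7), widens it to days 41 to 86 for analysis, and accepts readings in that range "provided that the subject remained off antihypertensive medication prior to collection of ABPM". The next paragraph reads "For the primary analysis, all available data will be used. There will be no imputation of data at 8 weeks". Section 5.2.3 agrees: "For the primary efficacy endpoint analysis, all available data will be used".

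Two of the further analyses in 5.4.1 take treated subjects out. Analysis 2: "Subjects who meet the protocol defined criteria for antihypertensive drug treatment and receive treatment within 8 weeks will be removed from the analysis". Analysis 3 also covers treatment for any reason, "or in whom antihypertensive medications are detected via compliance samples will be removed from the analysis".

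Section 5.2.8 describes the same extension but places the condition differently. It admits readings "beyond the protocol defined window to be analyzed, provided that the subject remains off antihypertensive medication prior to the visit assessments at 8 weeks".

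**Subgroup.** SAP 5.2.7 lists, for the primary endpoint in the ITT set, subjects who need a change of antihypertensive drugs at some point in follow-up after the procedure. Table 14.2.1-10 in SAP section 9 appears to be its output. No time limit is given, and the protocol follows subjects for 2 years.

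**Imputation.** Analysis 5 imputes both missing values and the values of treated subjects. It names no model and no covariates. Analysis 4, just above it, has a list of candidate covariates that includes 8-week office SBP.

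**The concern.** Two statements in 5.4.1 cannot both govern an on-drug ABPM taken on, say, day 56: the condition drops it and the data rule keeps it. A programmer working from 5.4.1 alone could report a different ITT primary estimate from one working from 5.2.3 and 5.2.8. The trial is meant to show whether the effect justifies a pivotal study, and 5 mmHg is its stated clinically meaningful difference.

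The subgroup raises a separate problem. Whether a subject needs drugs after the procedure depends on how blood pressure responded to the assigned procedure. Conditioning on it compares differently selected patients in the two arms. Only emergency drugs are allowed before week 8, so membership also depends on how much follow-up has accrued when the table is run. The same 8-week data could be split one way at the 8-week analysis and another way later.

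**Working it through.** **1. Days covered.** 56 − 7 = 49 and 56 + 7 = 63 give the protocol window. 56 − 15 = 41 and 56 + 30 = 86 give the analysis window. The added days are therefore 41–48 and 64–86. The sentence in 5.4.1 attaches its condition to 41–86, which contains 49–63.

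**2. Which reading fits the rest of the SAP.**

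| Place | If the condition covers days 41–86 | If it covers the added days only |
|---|---|---|
| 5.2.3 and 5.4.1, data rule | contradicted | kept inside the protocol window |
| 5.4.1, analysis 2 | largely repeats the primary | a distinct analysis |
| 4.1, drug use before the primary ABPM as a per-protocol exclusion | carried into ITT | stays per-protocol |
| 5.4.1, hierarchical analysis | uses 8-week change of two rescued subjects that the primary would discard | consistent |
| 5.2.8 | broader than its wording | matches |

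For secondary endpoints, 5.2.3 sets the two approaches next to each other as different analyses: "Analyses will be conducted with all available data and only in subjects who did not receive antihypertensive treatment between baseline and 8 weeks". So the SAP distinguishes them.

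Two loose ends remain. Section 5.4.1 does not say whether drug found only in a compliance sample breaks the off-drug condition, although analysis 3 counts it. For assigning the baseline value, 5.2.3 refers to "patients who meet the protocol defined criteria for antihypertensive drug treatment within the 8 weeks prior to assessment of the primary endpoint", whereas 5.4.1 also requires that treatment was received.

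**3. Scale.** With 40 evaluable subjects per arm, SE = SD × √(2/40). SD 8 gives 1.79, SD 10 gives 2.24 and SD 12 gives 2.68. As a check on these inputs, the plan's own figure is 80% power for 5.1 mmHg at SD 8: 5.1/1.789 = 2.851, and Φ(2.851 − 1.960) = 0.81 (0.80 with the t distribution). It is reproduced.

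**4. Keeping or dropping on-drug values.** The documents give no rescue rate and no drug effect, so everything here is assumed: true off-drug effect −5, SD 8, and rescue when off-drug change plus noise of SD 8 exceeds the sham 90th percentile.

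- SD of the rescue score: √(64 + 64) = 11.31. Sham cut-off z = 1.282. Treated cut-off z = 1.282 + 5/11.31 = 1.724, so 4.2% of the treated arm are rescued.
- Dropped: sham mean −(64/11.31) × 0.1755/0.90 = −1.10. Treated mean −5 − (64/11.31) × 0.0903/0.9576 = −5.53. Difference −4.43.
- Kept, with drug effect d: −5 + d × (0.100 − 0.0424). This gives −4.71, −4.42, −4.14 and −3.85 for d = 5, 10, 15 and 20.
- Kept minus dropped: −0.28, +0.01, +0.29 and +0.58 mmHg.

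A fuller simulation used ANCOVA on baseline, SD 8 to 12, drug effect 5 to 20 mmHg, rescue following Week 4 or 8-week office SBP, and up to half of rescued subjects' readings falling outside ± 7 days. It compared the added-days-only rule with the literal rule:

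| Sham rescued | Difference (mmHg) |
|---|---|
| 2% | −0.10 to +0.24 |
| 5% | −0.18 to +0.56 |
| 10% | −0.26 to +1.05 |

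Keeping on-drug values was nearer −5.0 in 26 of 36 scenarios at a 5 mmHg drug effect, 7 of 36 at 10, and none of 72 at 15–20. That is 33 of 144.

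**5. Subgroup.** Assume ambulatory change SD 10 and effect −5, office change SD 12 and effect −6, correlation 0.6 between the two changes, and drug need in the upper half of sham office change. The treated cut-off lies 6/12 = 0.5 SD above the treated mean, so 30.85% need drugs.

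- Need: treated −5 + 6 × 0.3521/0.3085 = +1.85. Sham 6 × 0.3989/0.5 = +4.79. Difference −2.94.
- No need: treated −5 − 6 × 0.3521/0.6915 = −8.05. Sham −4.79. Difference −3.27.

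Both fall short of −5. The same formulas give −3.97 and −4.13 at correlation 0.3, and −2.25 and −2.69 at 0.8. A simulation with need set by the 8-week office level (40–80% of sham) gave −4.6 to −2.9 in those needing drugs and −4.6 to −2.8 in the rest.

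**The case against.** The SAP largely answers the window question itself. Section 5.2.8 ties the condition to readings beyond the protocol window, 4.1 makes prior drug use a per-protocol exclusion, and the hierarchical analysis uses rescued subjects' values. That stands, and it is why the remedy is one corrected sentence and not a new primary analysis.

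The primary objective concerns efficacy without antihypertensive drugs, so excluding on-drug readings could be defended. That also stands, and the scenario counts lend it some support. But the SAP would then have to withdraw its all-available-data rule and analysis 2, so one rule must be written either way.

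Every size rests on assumed rescue rates, only emergency drugs are allowed before week 8, and the SAP plans no formal testing. This limits the importance of the point but does not remove the conflict.

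The subgroup is only to be presented, with no test specified, and the table shells, which are not in the supplied text, may define it further. A descriptive label does not remove the selection if the two arms are still set against each other within strata.

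On analysis 5, the natural reading carries over the covariates of analysis 4. That is plausible, so this remains a minor note.

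**Conclusion.** Two points hold, with minor to moderate weight. First, the sentence in 5.4.1 is wrong as written and conflicts with 5.2.3 and with the rest of 5.4.1. Under the stated assumptions the consequence is a few tenths of a mmHg, reaching about 1 mmHg only at 10% sham rescue, against a standard error of 1.8 to 2.7. Second, the 5.2.7 subgroup conditions on a response-driven event after randomisation. Under the assumptions shown, both strata can fall to about −2.3 to −4.6 when the overall effect is −5.

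Three stronger readings are not supported:

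- A reader might infer that the sponsor plans to exclude on-drug subjects from ITT. The SAP as a whole points the other way.
- A reader might infer that keeping in-window on-drug values gives a less biased off-drug effect. In 111 of the 144 scenarios it was not nearer (144 − 33). The case for the rewording is consistency alone.
- A reader might infer that analysis 5 is invalid. It is under-specified. It would carry a drug effect into the imputation only if a rescued subject's on-drug office SBP were used as a predictor, which the text does not settle.

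**What to change.** 1. Reword the window sentence in SAP 5.4.1 to match 5.2.8. ABPM on days 49 to 63 is analysed as randomised whatever the drug use. ABPM on days 41 to 48 or 64 to 86 is used only if the subject was off antihypertensive drugs before collection. The condition is still needed for the added days, because Protocol Table 1 (footnote 18) permits these drugs after the 8-week visit. State whether drug detected only in a compliance sample counts as being on drug, use one trigger in 5.2.3 and 5.4.1, and say that analyses 2 and 3 address the off-drug effect.
2. Remove the drug-change subgroup for the primary endpoint. If it is kept, fix its time limit and show it by arm as descriptive only, with no between-arm comparison.
3. As a minor addition, state the imputation model for analysis 5, and do not treat a rescued subject's on-drug 8-week office SBP as an off-drug value. The replacement predictor is for the sponsor to choose. Week 4 office SBP, for example, was further from the assumed truth than the on-drug value in 34 of 144 scenarios.

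Cost: SAP wording, minor programming, and one table lost or relabelled. Retained on-drug values can shrink the primary estimate: with a true effect of −5.0, the simulated results under this rule ran from −4.94 to −3.78 across 2–10% sham rescue.

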5.2. General Considerations

5.2.1. General Methods

Two unblinded team members (either two statisticians or a statistician and a statistical programmer) will be assigned for all analyses. This will allow for discussion of output and direct QC of statistical programming on the exact same dataset.

In general, continuous variables will be summarized with descriptive statistics (n, mean, SD, range, median, and interquartile range). The difference between groups will be presented and the normal approximation will be used to calculate two-sided 95% confidence intervals (CIs). Change from baseline, when relevant, will be computed as the paired mean difference and 95% CI of the mean difference at each time point.

For all continuous primary and secondary blood pressure endpoints, changes over time will be additionally explored in mixed effects repeated measures analyses, including the values at all time points.

Categorical variables will be summarized as frequencies and percentages. Relative risks and 95% CIs will be computed.

All statistical analyses will be performed using SAS® Version 9.4 or higher (SAS Institute, Cary, NC 27513, USA).

For each variable, the baseline value will be defined as the last value collected before the procedure.

There will be no formal hypothesis testing conducted in the study. Ninety-five percent CIs, when presented, are intended to be descriptive in nature only. For binary variables, CIs will be calculated via exact binomial methods. For continuous variables, the CI of the mean will be constructed using the normal approximation.

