5.6. Blood Pressure

Blood pressure will be summarized at each visit for the various blood pressure measures: office BP (Screening (Week -8), run-in (Week -2), baseline (Week -1), 4 weeks, 8 weeks, 3 months, 6 months, 1 year and 2 years), 24-hour ABPM (baseline [Week -1], 8 weeks, 6 months and 1 year), daytime ABPM (baseline [Week -1], 8 weeks, 6 months and 1 year) and nighttime ABPM (baseline [Week -1], 8 weeks, 6 months and 1 year). Both systolic and diastolic blood pressure will be presented separately. The mean values at each visit will be presented along with the mean change from baseline (and the matched baseline data for each visit).

The number and percentage of subjects with any decrease from baseline in the various blood pressure measures will be presented. The number and percentage of subjects with any, \geq 5 mmHg, \geq 10 mmHg, and \geq 20 mmHg decreases in blood pressure at each time point will be presented.

Ninety-five percent CIs for the change in mean blood pressure will be computed as well as the 95% CI for the percentage of subjects with any decrease in blood pressure.

These analyses will be conducted in the ITT analysis set.

In order to assess the totality of the data over time, changes in blood pressure at the 8-week, 3-month, 6-month, and 1-year and 2-year (office BP only) visits will be plotted over time by treatment group and assessed via a mixed effects repeated measures model. All available data at the time of analysis will be included in the model. This analysis will be conducted in the ITT analysis set with available data.

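### The named imputation covariates omit Week 4 office SBP, so the missing-data sensitivity analysis cannot reflect early blood pressure in subjects lost between Week 4 and Week 8; SAP 5.6 and 5.2.1 also disagree on whether Week 4 enters the office BP model

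*SAP*

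**What the plan says.** The primary ANCOVA in SAP 5.4.1 uses available data: "There will be no imputation of data at 8 weeks". Multiple imputation is a sensitivity analysis (items 4 and 5). Item 4 introduces its list with "The following covariates will be considered for the imputation: treatment group, age, gender, history of diabetes, BMI" and ends it with "baseline office systolic pressure, 8-week office systolic pressure, baseline 24-hour ambulatory SBP". Counting renal anatomy and number of baseline medications, there are ten covariates, and one of them (8-week office SBP) is measured after the procedure. Item 5 extends imputation to subjects given protocol-defined antihypertensive treatment and names no covariates of its own. SAP 5.5.2.1 and 5.5.2.2 repeat the sensitivity analyses for 8-week daytime, nighttime and office SBP.

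SAP 5.6 confirms that a Week 4 reading exists for office BP, "office BP (Screening (Week -8), run-in (Week -2), baseline (Week -1), 4 weeks, 8 weeks", but not for ABPM, "24-hour ABPM (baseline [Week -1], 8 weeks, 6 months and 1 year".

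On repeated measures, SAP 5.6 plots and models "changes in blood pressure at the 8-week, 3-month, 6-month, and 1-year and 2-year (office BP only) visits". SAP 5.2.1 describes "mixed effects repeated measures analyses, including the values at all time points", and the protocol synopsis says the same. SAP 5.6 also states that all available data go into the model.

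**The concern.** Multiple imputation adds information over an available-case analysis only if its predictors carry information about the missing outcome that the primary model lacks. For a subject lost after Week 4, the informative item is the blood pressure measured after the procedure and before leaving. If subjects who are off drug and running high tend to leave, and more of them are in one arm, the available-case difference is biased. An imputation built on arm and baseline data inherits that bias. The two analyses would then agree whether or not Week 4 blood pressure drove withdrawal, and a reader could take the agreement as evidence of robustness.

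The office SBP repeat is weaker still: the single post-baseline covariate on the list is the missing outcome itself, while the same measure four weeks earlier is unused.

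**Working it through.** **Who is affected.** Week 4 ± 7 days is days 21 to 35. The 8-week analysis window (SAP 5.2.8) is days 41 to 86, off drug. A Week 4 reading can therefore never serve as the 8-week office value. The gap covers subjects who leave after Week 4 and have no off-drug early-termination office reading from day 41 on. Subjects who attend Week 8 but lack a usable ABPM are not affected, because they have 8-week office SBP.

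**Why the imputation returns the primary result.** For affected subjects the imputed value comes from the regression of outcome on arm and baseline among those observed. Averaging over such values reproduces the observed-data coefficient for arm. Extra baseline covariates move it only slightly.

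**The plan's own figures.** 90 randomized and 80 evaluable implies 10 lost, 10/90 = 11.1%. The stated 80% power for 5.1 mmHg with SD 8 and 40 per arm reproduces (80.4%, noncentral t). This point changes neither. The documents give no split of losses by arm and no Week 4 to Week 8 correlation, so the rest is illustration.

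**Assumptions.** Correlation ρ of Week 4 office change with 8-week ABPM change, given baseline: 0.3 to 0.7. Log-odds of withdrawal rise by 1 or 2 per SD of Week 4 office BP. SD of the 8-week change is 8 mmHg (the plan's value) or 10.

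**Formula.** Let p be the fraction lost in an arm and m the mean standardized Week 4 value of those lost (by numerical integration). The observed arm mean is too low by ρ × SD × L, where L = m × p/(1−p). Bias in treatment minus sham = ρ × SD × (L_sham − L_treated).

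| Losses, treated vs sham | SD | Slope | L_treated | L_sham | Bias at ρ = 0.3 / 0.5 / 0.7 (mmHg) |
|---|---|---|---|---|---|
| 5 vs 5 of 45 | 8 | either | equal | equal | 0 / 0 / 0 |
| 6% vs 9% | 10 | 1 | 0.0560 | 0.0822 | 0.08 / 0.13 / 0.18 |
| 6% vs 9% | 10 | 2 | 0.0910 | 0.1301 | 0.12 / 0.20 / 0.27 |
| 2 vs 8 of 45 | 8 | 1 | 0.0421 | 0.1553 | 0.27 / 0.45 / 0.63 |
| 2 vs 8 of 45 | 8 | 2 | 0.0696 | 0.2360 | 0.40 / 0.67 / 0.93 |
| 0 vs 10 of 45 | 8 | 1 | 0 | 0.1910 | 0.46 / 0.76 / 1.07 |
| 0 vs 10 of 45 | 8 | 2 | 0 | 0.2871 | 0.69 / 1.15 / 1.61 |

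Worked case (2 vs 8, slope 1, ρ = 0.5): L_sham = 0.718 × 8/37 = 0.155; L_treated = 0.905 × 2/43 = 0.042; bias = 0.5 × 8 × 0.113 = 0.45.

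With a true difference of −5, positive bias is attenuation.

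**Simulation check.** 400,000 per arm, true difference −5, SD 10, about 6% versus 9% lost. The available-case ANCOVA and the imputation without Week 4 both gave −4.85, −4.84 and −4.77 at ρ = 0.3, 0.5 and 0.7. Adding Week 4 gave −4.96, −5.03 and −5.04, so the shifts are 0.11, 0.19 and 0.27. In the 45-per-arm scenarios, adding Week 4 brought the simulated bias to about 0 throughout.

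**Against sampling error.** With 40 per arm the standard error is SD × √(2/40): 2.24 mmHg for SD 10 and 1.79 for SD 8. The 6% versus 9% shifts are 0.11/2.24 = 0.05 to 0.27/2.24 = 0.12 standard errors. The largest 2 versus 8 bias is 0.93/1.79 = 0.52.

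**Repeated measures.** Office BP has a Week 4 value. SAP 5.2.1 and the protocol would include it, and the 5.6 visit list leaves it out. For ABPM there is no Week 4 value, so starting at Week 8 is correct.

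**The case against.** The strongest reply is that this is small and confined. The primary ANCOVA involves no imputation, SAP 5.2.1 and 5.2.6 disclaim formal hypothesis testing, and moderate losses shift the estimate by about a tenth of a standard error or less. That stands, and it limits the weight of the point.

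Subjects running high before Week 8 can also receive emergency treatment without leaving. SAP 5.4.1 covers them in items 1, 2, 3 and 5 and in the rescue-first win ratio. This stands for rescued subjects, though not for those who withdraw. If item 5 borrows item 4's list, its only post-baseline predictor for a rescued subject was measured after rescue.

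Item 4 says its covariates will be considered, so the list is not stated to be closed. That is fair, but it leaves the choice open and does not name the most relevant omitted variable.

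Four stronger readings are tempting, and the documents do not support them:

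- A reader might infer that Week 4 is the only blood pressure before Week 8. Protocol Table 1, footnotes 19 and 20, adds cuff readings on Days 0 and 1 and a twice-daily diary, and an early-termination office reading may exist. Week 4 is the only scheduled office BP visit between the procedure and Week 8.
- A reader might infer that the repeated-measures model firmly excludes Week 4. SAP 5.2.1, the protocol and the all-available-data sentence in 5.6 point the other way, so this is an inconsistency. SAP 5.6 also gives that model the purpose of viewing all the data over time, not of testing withdrawal.
- A reader might infer that the omission inflates the apparent benefit. If sham loses more high-BP subjects, it understates it. The sign reverses only if the treated arm loses more.
- A reader might infer that Week 4 data would account for every reason for leaving. They account only for withdrawal related to that reading.

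**Conclusion.** The point holds as a modest, specific weakness in the sensitivity analyses, together with a wording conflict between SAP 5.6 and 5.2.1 for office BP. For subjects lost between Week 4 and Week 8 without a qualifying early-termination reading, the named imputation model cannot depart systematically from the primary result, so agreement between the two is uninformative about BP-related withdrawal.

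The likely size is small: attenuation of about 0.1 to 0.3 mmHg at 6% versus 9% losses, about 0 if losses balance, and about 0.3 to 0.9 mmHg if the planned ten losses split 2 versus 8. The 1.6 mmHg corner needs all ten losses in sham and the strongest assumed dependence. The comparison is with the 5 mmHg that the plan considers clinically meaningful. These figures rest on the assumed correlation, withdrawal slope and split of losses; they are a range, not a forecast. The case for acting is that the data are already collected and the better model costs nothing.

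**What to change.** 1. In SAP 5.4.1 item 4, name Week 4 office SBP as an imputation covariate, and early-termination office SBP where obtained. For the ABPM outcomes it enters as an auxiliary variable.
2. State that item 5, and the repeats for 8-week daytime, nighttime and office SBP in 5.5.2.1 and 5.5.2.2, use the same covariates. In the office SBP repeat, 8-week office SBP is the outcome and drops off the predictor list.
3. In SAP 5.6, add Week 4 to the visits in the repeated-measures model for office SBP and DBP, to match 5.2.1 and the protocol. Leave the ABPM models starting at Week 8.

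The cost is a few lines of SAP text and an entry in its change log. No new data, visits or sample size are needed, and the primary analysis is unchanged.
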